2.3.1.2 Potential risks of pembrolizumab

Pembrolizumab is a PD-1 blocking antibody indicated in more than 12 different tumors and lines of treatment (including NSCLC and CRC).

The Warning and precautions for pembrolizumab include immune-mediated reactions which may be severe or fatal, can occur in any organ system or tissue, including the following:

immune-mediated pneumonitis, colitis, hepatitis, endocrinopathies, nephritis with renal dysfunction, dermatologic adverse reactions including Stevens Johnson syndrome and toxic epidermal necrolysis and solid organ transplant rejection. It includes infusion related reaction, embryofetal toxicity and complications of allogeneic hematopoietic stem cell transplantation (HSCT). Treatment of patients with multiple myeloma (MM) with a PD-1 or PD-L1 in combination with a thalidomide analogue plus dexamethasone is not recommended outside of controlled clinical trials.

The most common adverse reactions (reported in $\geq 20\%$ of patients) are for pembrolizumab as single agent: fatigue, musculoskeletal pain, decreased appetite, pruritus, diarrhea, nausea, rash, pyrexia, cough, dyspnea, constipation, pain, and abdominal pain. For pembrolizumab in combination with chemotherapy are: fatigue/asthenia, nausea, constipation, diarrhea, decreased appetite, rash, vomiting, cough, dyspnea, pyrexia, alopecia, and peripheral neuropathy and for pembrolizumab in combination with axitinib are: diarrhea, fatigue/asthenia, hypertension, hepatotoxicity, hypothyroidism, decreased appetite, palmar-plantar erythrodysesthesia, nausea, stomatitis/mucosal inflammation, dysphonia, rash, cough, and constipation.

Pembrolizumab has been approved for use at an additional recommended dosage of 400 mg every 6 weeks for all approved adult indications. Based on the modeling of dose/exposure efficacy and safety relationships and observed pharmacokinetic data from an interim analysis of 41 patients with melanoma treated with pembrolizumab 400 mg every 6 weeks, there are no anticipated clinically significant differences in efficacy and safety between pembrolizumab doses of 200 mg or 2 mg/kg every 3 weeks or 400 mg every 6 weeks.

Refer to Pembrolizumab US Package Insert and summary of product characteristics (SmPC) for details and the most recent information.

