5.1 INCLUSION CRITERIA

Participants are eligible to be included in the study only if all of the following criteria apply:

Age

I 01. All participants must be ≥ 18 years of age (or country's legal age of majority if > 18 years), at the time of signing the informed consent.

Type of participant and disease characteristics

I 02. Part-1 and Part-4 participants should have histologically or cytologically proven diagnosis of non-squamous NSCLC with metastatic disease progression after platinum-based chemotherapy and ICI irrespective of the sequence, ie, either concurrently or sequentially:

- At least one prior line of treatment in a metastatic setting
- Relapse to develop metastatic disease during or within 6 months of an adjuvant/neoadjuvant treatment (to be considered as first-line treatment), OR
- Disease progression after or during one platinum-based chemotherapy and one ICI (anti-PD1/PD-L1) irrespective of the sequence, ie, concurrently or sequentially.

OR

Histologically proven diagnosis of advanced solid tumors including CRC that have failed, are intolerant to or are considered ineligible for SoC anti-cancer treatments including approved drugs for oncogenic drivers in their tumor type.

I 03. Part-1 participants must have one or more of the following molecular aberrations:

- KRAS^{G12C} mutations (NSCLC, CRC and any other histotype)
- KRAS^{G12A}, KRAS^{G12D}, KRAS^{G12S}, KRAS^{G12V} mutations (NSCLC)
- KRAS^{G12A}, KRAS^{G12D}, KRAS^{G12S}, KRAS^{G12V} and/or MSI-H or dMMR (CRC)
- KRAS amplification (any histotype)
- NF1 LOF (any histotype)
- BRAF Class 3 mutations (any histotype)

I 04. All participants should have at least 1 measurable disease per RECIST v1.1. An irradiated lesion can be considered measurable only if progression has been demonstrated on the irradiated lesion.

I 05. All participants should have Eastern Cooperative Oncology Group (ECOG) performance status 0-1.

Sex

I 06. All (male or female) participants

Contraceptive use by men or women should be consistent with local regulations regarding the methods of contraception for those participating in clinical studies.

a) Male participants

A male participant must agree to use contraception (see Appendix 4 [[Section 10.4](#)]) during the intervention period and for at least 4 months (6 months for Part-3) after the last dose of study intervention.

b) Female participants

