A female participant is eligible to participate if she is not pregnant (see Appendix 4 [[Section 10.4](#)]), not breastfeeding, and at least one of the following conditions applies:

- Not a woman of childbearing potential (WOCBP) as defined in Appendix 4 [[Section 10.4](#)]).

OR

- A WOCBP who agrees to follow the contraceptive guidance in Appendix 4 [[Section 10.4](#)]) during the intervention period and for at least 4 months (6 months for Part-3) after the last dose of study intervention.

Informed Consent

I 07. All participants should be capable of giving signed informed consent as described in Appendix 1 of the protocol which includes compliance with the requirements and restrictions listed in the informed consent form (ICF) and in this protocol.

Part-2 (new criteria added with amendment 03)

I 08. Cancer diagnosis at study entry:

For participants in Cohorts A, - histologically or cytologically confirmed diagnosis of Stage IV (per American Joint Committee on Cancer [AJCC] 8th edition [112]) NSCLC.

I 09. For Part-2, PD-L1 expression TPS as determined (with an absolute value provided to Sponsor) at local laboratory.

- Cohort A1: PD-L1 expression TPS $\geq 50\%$,
- Cohort A2: PD-L1 expression TPS 1%-49%.

I 10. Provision of tumor tissue:

- Mandatory for participants enrolled with local PD-L1 testing. Baseline tumor tissue or slides should be provided for central lab retrospective analysis. Archival tumor tissue samples should be obtained from biopsies done within 6 months, and there should be no systemic anti-cancer therapy between collection of biopsy and enrollment. Slides specifications are detailed in Lab Manual.

I 11. Prior anticancer therapy

- For participants in Cohorts A1 and A2 - Have not received prior systemic therapy for advanced/metastatic NSCLC. Participants who received adjuvant or neoadjuvant therapy are eligible if the adjuvant/neoadjuvant therapy was completed at least 6 months prior to the development of metastatic disease.

Part-3 (new criteria added with amendment 04)

I 12. Participants with histologically or cytologically proven metastatic NSCLC with at least one prior line of treatment in a metastatic setting. Prior KRAS G12C targeted therapy is acceptable (only in Part-3A)

I 13. Participants must have following molecular aberration tested at the local laboratory:

- KRAS G12C mutation assessed by a local Sponsor-approved test. Approved test list can be found in eCRF.

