6.3 MEASURES TO MINIMIZE BIAS: RANDOMIZATION AND BLINDING

This is an open label study without randomization. No blinding or randomization will be used for this study. In order to minimize bias, the participants will be assigned sequentially as they are enrolled into the study using the inclusion and exclusion criteria as outlined in [Section 5.1](#) and [Section 5.2](#). Enrollment will be confirmed by the sponsor Medical Monitor after review of all supporting documentation for eligibility criteria.

Participants will be allocated a screening number at the time of signing the ICF. If a participant is a screen failure, the number will not be reassigned.

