10.4 APPENDIX 4: CONTRACEPTIVE GUIDANCE AND COLLECTION OF PREGNANCY INFORMATION

DEFINITIONS

Contraceptive use by men or women should be consistent with local regulations regarding the methods of contraception for those participating in clinical studies.

A male participant must agree to use contraception during the intervention period and for at least 6 months after the last dose of study intervention.

A female participant is eligible to participate if she is not pregnant, not breastfeeding, and at least one of the following conditions applies:

- Not a WOCBP OR
- A WOCBP as defined below who agrees to follow the contraceptive guidance during the intervention period and for at least 6 months after the last dose of study intervention as described below.

Woman of childbearing potential (WOCBP)

A woman is considered fertile following menarche and until becoming post-menopausal unless permanently sterile (see below).

If fertility is unclear (eg, amenorrhea in adolescents or athletes) and a menstrual cycle cannot be confirmed before first dose of study intervention, additional evaluation should be considered.

Women in the following categories are not considered WOCBP

1. Premenarchal
2. Premenopausal female with 1 of the following:
 - Documented hysterectomy
 - Documented bilateral salpingectomy
 - Documented bilateral oophorectomy

For individuals with permanent infertility due to an alternate medical cause other than the above, (eg, mullerian agenesis, androgen insensitivity), Investigator discretion should be applied to determining study entry.

Note: Documentation can come from the site personnel's: review of the participant's medical records, medical examination, or medical history interview.

3. Postmenopausal female

- A postmenopausal state is defined as no menses for 12 months without an alternative medical cause.
- A high follicle-stimulating hormone (FSH) level in the postmenopausal range may be used to confirm a postmenopausal state in women not using hormonal contraception or hormone replacement therapy (HRT). However, in the absence of 12 months of amenorrhea, confirmation with more than one FSH measurement is required.
- Females on HRT and whose menopausal status is in doubt will be required to use one of the non-estrogen hormonal highly effective contraception methods if they wish to continue their HRT during the study. Otherwise, they must discontinue HRT to allow confirmation of postmenopausal status before study enrollment.

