CONTRACEPTION GUIDANCE:

COLLECTION OF PREGNANCY INFORMATION:

Male participants with partners who become pregnant

- The Investigator will attempt to collect pregnancy information on any male participant's female partner who becomes pregnant while the male participant is in this study. This applies only to male participants who receive study intervention.
- After obtaining the necessary signed informed consent from the pregnant female partner directly, the Investigator will record pregnancy information on the appropriate form and submit it to the Sponsor within 24 hours of learning of the partner's pregnancy. The female partner will also be followed to determine the outcome of the pregnancy. Information on the status of the mother and child will be forwarded to the Sponsor. Generally, the follow-up will be no longer than 6 to 8 weeks following the estimated delivery date. Any termination of the pregnancy will be reported regardless of fetal status (presence or absence of anomalies) or indication for the procedure.

Female participants who become pregnant

- The Investigator will collect pregnancy information on any female participant who becomes pregnant while participating in this study. The initial information will be recorded on the appropriate form and submitted to the Sponsor within 24 hours of learning of a participant's pregnancy.
- The participant will be followed to determine the outcome of the pregnancy. The Investigator will collect follow-up information on the participant and the neonate and the information will be forwarded to the Sponsor. Generally, follow-up will not be required for longer than 6 to 8 weeks beyond the estimated delivery date. Any termination of pregnancy will be reported, regardless of fetal status (presence or absence of anomalies) or indication for the procedure.
- Any pregnancy complication or elective termination of a pregnancy for medical reasons will be reported as an AE or SAE.

- A spontaneous abortion (occurring at <22 weeks gestational age) or still birth (occurring at >22 weeks gestational age) is always considered to be an SAE and will be reported as such.
- Any post-study pregnancy related SAE considered reasonably related to the study intervention by the Investigator will be reported to the Sponsor as described in [Section 8.3.4](#). While the Investigator is not obligated to actively seek this information in former study participants, he or she may learn of an SAE through spontaneous reporting.

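### Inclusion criterion I06 asks for 4 months of contraception after the last dose in Parts 1, 2 and 4, while Appendix 4, which it cites, asks for 6 months in every Part

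*Protocol*

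**What the plan says.** Criterion I06 in Protocol Section 5.1 covers all participants, male and female. Limb (a), for men, refers to Appendix 4 for contraception and sets the period as "for at least 4 months (6 months for Part-3) after the last dose of study intervention". Limb (b) admits a WOCBP if she agrees to follow the guidance in Appendix 4 "during the intervention period and for at least 4 months (6 months for Part-3) after the last dose of study intervention".

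Appendix 4 (Section 10.4) restates the same condition with a different period. Each man "must agree to use contraception during the intervention period and for at least 6 months after the last dose of study intervention". For women, a WOCBP is eligible if she is one "who agrees to follow the contraceptive guidance during the intervention period and for at least 6 months after the last dose of study intervention". Neither sentence names a Part.

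Two other provisions bear on the point. Criterion I07 ties consent to "compliance with the requirements and restrictions listed in the informed consent form (ICF) and in this protocol". Section 6.3 provides a central check: "Enrollment will be confirmed by the sponsor Medical Monitor after review of all supporting documentation for eligibility criteria".

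**The concern.** The two places give different minimum periods for the same obligation in Parts 1, 2 and 4. I06 relies on Appendix 4, and Appendix 4 is itself worded as an eligibility condition, so the mismatch is between two operative rules and not between a rule and background text. The introduction to Section 5 does not permit waivers of enrollment criteria, so the criterion needs a single reading.

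What is at stake is a safety instruction to participants. Section 2.3.1.2 lists embryofetal toxicity among the pembrolizumab warnings, and pembrolizumab is the combination drug in exactly the Parts where the texts disagree. A site working from I06 alone could release participants from contraception 2 months before the Appendix 4 minimum. Section 8.3.5 collects pregnancy details only until the end-of-treatment visit, about 30 days after the last dose. A pregnancy in the disputed months would therefore fall outside the collection period set there.

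**Working it through.** No statistical figure is involved. The check sets the current texts side by side and takes the difference.

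**Inputs**
- I06 (a), men: 4 months, or 6 months in Part-3 (Section 5.1).
- I06 (b), WOCBP: 4 months, or 6 months in Part-3 (Section 5.1).
- Appendix 4, men: 6 months, no Part named (Section 10.4).
- Appendix 4, WOCBP: 6 months, no Part named (Section 10.4).

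**Comparison** (minimum months after the last dose; difference = Appendix 4 minus I06)

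| Part | Combination drug | I06 | Appendix 4 | Difference |
|---|---|---|---|---|
| 1 | pembrolizumab | 4 | 6 | 6 − 4 = 2 |
| 2 | pembrolizumab | 4 | 6 | 6 − 4 = 2 |
| 3 | adagrasib | 6 | 6 | 6 − 6 = 0 |
| 4 | pembrolizumab | 4 | 6 | 6 − 4 = 2 |

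The result is the same for men and for WOCBP.

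**Can both rules be met at once?** Yes. Both are minimums, and 6 months satisfies each. The conflict appears when a participant in Part 1, 2 or 4 agrees to at least 4 but fewer than 6 months: I06's stated period is met and Appendix 4's is not.

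**Does the protocol say which applies?** Not expressly. I07 can be read as favoring the stricter period, because it ties consent to the restrictions anywhere in the protocol, but it is not a precedence rule.

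**Does the finding depend on the amendment log?** No. Both periods stand in current text. As background only, the log records that Appendix 4 was raised from 4 to 6 months, with no Part limit, for consistency with similar protocols. It also records that I06 was among the criteria updated to show which Part they apply to. The two entries point in different directions, so they do not show which period the sponsor intends for the pembrolizumab Parts.

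**How many participants?** This cannot be derived. Women who are not WOCBP are exempt, and the documents give no expected mix by sex or childbearing potential. Section 4.3 describes the 200 mg dose as already selected as the RP2D with pembrolizumab. Part-1 is therefore probably past most enrollment, and for that Part the point mainly concerns instructions after treatment. This is an inference, because the section does not state Part-1 enrollment status.

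**The case against.** The strongest reply is that the texts are compatible. Both say at least, both limbs of I06 send the reader to Appendix 4, and I07 adds compliance with the protocol's restrictions. A careful site would arrive at 6 months. I06 also does not tell anyone to stop at 4 months. This stands as a reason to expect little harm in practice. It does not remove the conflict, because I06 prints 4 months in the criterion that sites apply and nothing states that the appendix overrides it.

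The safety link can also be called thin. The protocol lists embryofetal toxicity for pembrolizumab but gives no period tied to it, and nothing in the documents shows that 4 months is too short. That is correct. The finding is that the instruction is contradictory, not that 4 months is unsafe.

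The Part split in I06 may be deliberate, since only Part-3 uses adagrasib, in which case Appendix 4 is the text that is too general. The documents do not settle this, so the fix below allows for either intention.

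Some text is unseen. The content under the heading "CONTRACEPTION GUIDANCE" in Appendix 4 is missing from the available copy, and the consent form is not among the documents. Either may already state one period. This limits what can be said about the instruction participants actually receive. The two eligibility statements would still disagree and need aligning.

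Finally, the Medical Monitor's confirmation of each enrollment lowers the chance that sites diverge. It does not say which period to check against, and it does not reach advice given after treatment ends.

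**Conclusion.** The inconsistency is real. For men and WOCBP in Parts 1, 2 and 4 the two current minimums differ by 2 months (4 against 6); in Part-3 they agree. The mismatch between the visible texts is certain. Its practical effect is not, because it depends on the unseen guidance text and consent form, on how sites read the cross-reference, and on an unknown number of affected participants. If Part-1 enrollment is largely over, the practical reach is mainly Parts 2 and 4.

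No endpoint, analysis population, sample size or analysis changes. The point still deserves correction because it concerns a participant-safety instruction that is also an eligibility condition.

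**What to change.** Change I06 (a) and (b) to require contraception for at least 6 months after the last dose in all Parts, and align the consent form if it states anything else. This satisfies Appendix 4 as it stands and needs no change there.

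If the sponsor intends 4 months for the pembrolizumab Parts and can justify it, keep I06 and add the same Part split to both Appendix 4 sentences, for men and for WOCBP.

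The first option costs an edit to two sentences, a possible consent-form update, and 2 more months of contraception for some participants in Parts 1, 2 and 4. Participants in those Parts who have already been given the 4-month period should be told of the change.

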5.2 EXCLUSION CRITERIA

Participants are excluded from the study if any of the following criteria apply:

Medical conditions

E 01. Predicted life expectancy \leq 3 months.

E 02. Primary central nervous system (CNS) tumors.

E 03. Known or suspected leptomeningeal or brain metastases, symptomatic or impending spinal cord compression. Participants previously treated for these conditions who have had stable CNS disease (eg, no evidence of clinical and radiographic disease progression and asymptomatic in the absence of corticosteroids or anti-convulsant therapy over the previous 4 weeks) are eligible.

E 04. History of cerebrovascular stroke or transient ischemic attack within previous 6 months.

E 05. Prior solid organ or hematologic transplant.

E 06. The following ocular abnormalities are excluded:

- a) History or current retinal pigment epithelial detachment (RPED), central serous retinopathy, RVO, neovascular macular degeneration, or factors considered by the Investigator to present an unacceptable risk of RPED or RVO.
- b) Visible retinal pathology as assessed on ophthalmic examination that is considered a significant risk factor for RVO or RPED by an ophthalmologist.

E 07. Any of the following cardiovascular abnormalities:

- a) Symptomatic congestive heart failure, New York Heart Association Class II or higher
- b) Acute coronary syndrome (eg, unstable angina, coronary artery stenting, or angioplasty, bypass grafting) within prior 6 months
- c) History or current uncontrolled clinically significant unstable arrhythmias
- d) Participants who have pacemakers to control atrial arrhythmias are candidates for the study. Participants with medically controlled atrial fibrillation >6 months prior to C1D1 are eligible.
- e) History of congenital long QT syndrome or prolonged QTcF interval >480 msec using Fridericia's formula (unless a pacemaker is in place) or uncorrectable abnormalities in blood electrolytes (sodium, potassium, calcium, magnesium, phosphorus).
- f) Left ventricular ejection fraction (LVEF) < institutional LLN or <50%, whichever is lower.

E 08. Treatment-related immune-mediated (or immune-related) AEs from immune-modulatory agents (including but not limited to anti-PD 1/PD-L1 agents and anti-CTLA 4 monoclonal antibodies) that caused permanent discontinuation of the agent, or that were Grade 3 or 4 in severity, or that have not resolved to baseline at least 3 months prior to initiation of IMP. For other agents, treatment related immune mediated (or immune related) AEs that were Grade 2 or above (applies to Part-1, Part-2, and Part-4).

E 09. Ongoing AEs (excluding alopecia and fatigue) caused by any prior anti-cancer therapy \geq Grade 2 (NCI-CTCAE Version 5.0).

E 10. Active, known or suspected autoimmune disease that has required systemic treatment in the past 2 years (ie, with use of disease modifying agents, corticosteroids or immunosuppressive drugs), except for replacement therapy (eg, thyroxine, insulin, or physiologic corticosteroid replacement) (applies to Part-1, Part-2 and Part-4).

E 11. History of or current interstitial lung disease, active pneumonitis, or pneumonitis that requires oral or IV glucocorticoids to assist with management (radiation pneumonitis in the radiation field is permitted; radiation pneumonitis that requires steroids is not permitted); history of thoracic radiation therapy of >30 Gy within 6 months of the first dose of trial treatment.

E 12. Receipt of a live-virus vaccination within 28 days of planned treatment start. Receipt of viral vaccine that do not contain live virus within 7 days. Seasonal flu vaccines that do not contain live virus are permitted.

- E 13. Known infection with human immunodeficiency virus (HIV), known uncontrolled hepatitis B virus (HBV) infection, known uncontrolled hepatitis-C virus (HCV) infection, active tuberculosis, or severe infection requiring parenteral antibiotic treatment. To control HBV infection, participants with positive hepatitis B surface antigen (HBsAg) should have started anti-HBV therapy before initiation of IMP, and the screening HBV viral load should be <2000 IU/mL (10⁴ copies/mL). The anti-HBV therapy should continue throughout the treatment period. The HCV-treated participants must have completed their treatment at least 1 month prior to starting study intervention. Participants with positive HCV antibody and undetectable HCV RNA without anti-HCV therapy are eligible.
- E 14. Known second malignancy either progressing or requiring active treatment within the last 3 years (except for basal cell carcinoma of the skin, squamous cell carcinoma of the skin, ductal carcinoma in situ (DCIS) of the breast, or in situ cervical cancer that has undergone potentially curative therapy).
- E 15. Impairment of gastrointestinal function that may alter the absorption of SAR442720 (eg, uncontrolled nausea and vomiting, diarrhea, malabsorption syndrome, inflammatory bowel disease, gastrectomy, small bowel resection).
- E 16. History of severe allergic reaction to any of the study intervention components.

Prior/concomitant therapy

- E 17. Last administration of prior anti-tumor therapy (chemotherapy, targeted agents, and immunotherapy) or any investigational treatment within 28 days or less than 5 times the half-lives of the agent (whichever is shorter) prior to the first dose of IMP.
- E 18. Participant who has received prior radiotherapy within 2 weeks of start of study intervention. Participants must have recovered from all radiation-related toxicities, not require corticosteroids, and not have had radiation pneumonitis. A 1-week washout is permitted for palliative radiation (≤ 2 weeks of radiotherapy) to non-CNS disease.
- E 19. Comorbidity requiring corticosteroid therapy (>10 mg prednisone/day or equivalent) within 14 days of IMP initiation. Physiologic replacement doses are allowed even if they are >10 mg of prednisone/day or equivalent, as long as they are not being administered for immunosuppressive intent. Inhaled or topical steroids are permitted, provided that they are not for treatment of an autoimmune disorder.
- E 20. Major surgery ≤ 28 days or non-study related minor procedures (eg, Port-a-Cath placement) ≤ 7 days prior to C1D1. In all cases, the participant must be sufficiently recovered and stable before treatment administration.
- E 21. Any other unstable or clinically significant concurrent medical condition (eg, substance abuse, uncontrolled intercurrent illness including active infection, arterial thrombosis, and symptomatic pulmonary embolism, etc) that would, in the opinion of the investigator, jeopardize the safety of a participant, impact their expected survival through the end of the study participation, and/or impact their ability to comply with the protocol.

E 22. Medication and supplements that may interfere or potentiate with SAR442720 and/or adagrasib metabolism or toxicity PRIOR or DURING study intervention are excluded:

- Strong CYP3A4 inducers or inhibitors (within 7 days prior)
- Strong P-glycoprotein (P-gp) inhibitors (eg, cyclosporine, tacrolimus; within 7 days prior)
- Strong Breast Cancer Resistance Protein (BCRP) inhibitors (eg, eltrombopag; within 7 days prior) (applies to Part-3 only)
- Proton pump inhibitors (within 3 days prior) or H2-receptor antagonists (within 1 day prior) during the dose escalation portion of the study
- Medications known to prolong QTc interval
- Acetylsalicylic acid (low dose aspirin, anticoagulation with low-molecular weight heparin or direct Factor X inhibitors and LMWH are allowed. Prophylactic LMWH is also allowed for high risk patients with hypercoagulability).

Diagnostic assessments

E 23. Inadequate organ and bone marrow function at the Screening visit:

- Absolute neutrophil count (ANC) $<1000 \mu\text{L} (1 \times 10^9/\text{L})$.
- Platelets $<100 \times 10^3 \mu\text{L}$ (after at least 3 days without platelet transfusion).
- Hemoglobin $<9 \text{ g/dL}$ or $<5.6 \text{ mmol/L}$ (without transfusions within 2 weeks of initiation of IMP).
- Total bilirubin $>2 \times \text{ULN}$.
- AST and/or ALT $>3 \times \text{ULN}$ (or $>5 \times \text{ULN}$ for participants with liver metastases).
- Blood creatinine $>1.5 \times \text{ULN}$ or creatinine clearance of $<50 \text{ mL/min}$ (using Cockcroft Gault formula or 24-hour urine collection)
- Prothrombin time (PT)/international normalized ratio (INR) and activated partial thromboplastin time or partial thromboplastin time (aPTT/PTT) $>1.3 \times \text{ULN}$ or outside the therapeutic range of the local laboratory if receiving therapeutic anticoagulation that would affect the PT/INR.

Other exclusions

E 24. Individuals accommodated in an institution because of regulatory or legal order; prisoners or participants who are legally institutionalized.

E 25. Participant not suitable for participation, whatever the reason, as judged by the Investigator, including medical or clinical conditions, or participants potentially at risk of noncompliance to study procedures.

- E 26. Participants are employees of the clinical study site or other individuals directly involved in the conduct of the study, or immediate family members of such individuals (in conjunction with Section 1.61 of the International Council for Harmonisation (ICH)-Good Clinical Practice (GCP) Ordinance E6).
- E 27. Any specific situation during study implementation/course that may rise ethics considerations.
- E 28. Sensitivity to any of the study interventions, or components thereof, or drug or other allergy that, in the opinion of the Investigator, contraindicates participation in the study.

Tumor characteristics for Part-2, Part-3, and Part-4 (new criteria added with amendment 03):

- E 29. Following known genotypes are excluded for expansion cohorts:
 - a) NRAS (except G12A/C)
 - b) RASQ61
 - c) KRASG13
 - d) BRAF Class 1, 2, or unclassified
 - e) PIK3CA

New criteria added with amendment 04

- E 30. Subject has a known activating SHP2 mutation (eg, Noonan syndrome)
- E 31. Treatment with following agents in Part-3 only:
 - KRAS G12C inhibitors (Part-3B only)
 - SHP2 inhibitors (Part-3B only)
 - CYP3A substrates with a narrow therapeutic index

